## **8 ASSIGNMENT OF STUDY TREATMENT**

### **8.1 Randomization**

After obtaining informed consent a consecutive screening number will be assigned to each patient according to the sequence of study entry, from S001 onwards (S002, S003 etc.). After confirming eligibility for the study, patient will be randomized (2:1 to rhNGF eye drops solution at 20 µg/ml (120 patients) or vehicle eye drops solution (60 patients) to be administered 6 times per day per study eye (or both eyes if applicable) for 8 weeks) and allocated with a consecutive randomization number of the randomization list starting with 001 onwards (002, 003 etc.).

### **8.2 Treatment allocation**

After successful completion of screening each eligible patient will be assigned a patient number (randomization number) according to the sequence of study entry (randomization), from 001 to 180. Drop outs will not be replaced after randomization.

### **8.3 Masking**

For the whole duration of the trial treatments will be unknown to the patient, the Investigator and the site staff. The identity of the treatments will remain unknown to the patient, Investigator, site staff and Sponsor's clinical research personnel until the study is unmasked for the final statistical analysis (data base lock) except in case of specific events that will require unmasking of the patient.

The vials of rhNGF (20 µg/ml) and the vials containing the vehicle of rhNGF will be identical in appearance and the contents of the vials will be indistinguishable. All staff who is directly involved in the analysis of study results will remain masked to treatment assignments while the study is in progress.

A list of sequential kit numbers will be generated by a member of the CRO SAS programming group not involved in the conduct of the study. Each kit number will be randomly associated with a treatment group. Patients will be assigned to treatment in numerical order. A tear-off label from the kit box, with the kit number, will be attached to the investigational product dispensing log.

If the Investigator becomes unmasked for any reason, this information will be recorded on source data and in the eCRF of the study, specifying the date and the reason.

In the event of a medical emergency where the knowledge of patient treatment is required to provide the patient with appropriate care, Investigators will have the possibility to unmask the treatment assignment for a specific patient. If there is sufficient time, the Investigators are encouraged to contact the CRO staff to discuss individual case before unmasking concerned patient.

## **9 EVALUATION PARAMETERS**

### **9.1 Study variables**

#### **9.1.1 Primary variables**

- Treatment-emergent adverse events (TEAEs), assessed throughout the study
- Symptom Assessment in Dry Eye (SANDE) – mean changes from baseline will be evaluated for severity and frequency (for primary week 8 endpoint analysis, LOCF will be imputed for early end-of treatment data)

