#### **9.1.2 Co-primary variable**

- Cornea vital staining with fluorescein (National Eye Institute [NEI] scales) – mean changes from baseline will be evaluated at week 8 for Co-primary endpoint analysis, LOCF will be imputed for early end-of treatment data)

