3.7 Changes in the Conduct of Study or Planned Analysis compared to protocol/CIP

This SAP implements the subsequent deviations and clarifications from the analysis specification of the study protocol:

- For the SAP, study endpoints are presented as provided in the protocol synopsis and protocol section 2 (study objectives).
- Definition of Screen Failures. In the study protocol (section 10.1.1) a screen failure is defined as patient who is not eligible, i.e. is not respecting all the inclusion/exclusion criteria. According to the study protocol, such patients should not be randomized and enrolled.
To streamline presentation of patient flow for reporting and to extend definition also for protocol deviations, screen failure will be defined as screened patients, who are not randomized. By this, patients, who were randomized although they did not comply with eligibility criteria will not be considered as screen failure. On the contrary, patients, who comply with all eligibility criteria but dropped out from the study before randomization (e.g. due to consent withdrawal) will be considered as screen failure.
- Definition of compliance: in section 10.3, the study protocol demands further compliance definitions based on diary card information to investigate compliance with study eye treatment. However, as no eye-specific assessments were recorded on diary card, no such definitions were established.
- In the study protocol, no inferential analyses are specified. However, purely exploratory 95% confidence intervals and hypothesis testing for the difference between treatment groups will be implemented in the SAP on sponsor's request. These inferential procedures will be purely exploratory without adjusting for type I error rate.

4 General Definitions

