8.2 Specific Methods for Efficacy Analyses

As a general principle, all efficacy analyses will be performed on a patient-level, considering the Main Eye for the analysis of Co-Primary and Secondary efficacy endpoint. Efficacy data in Secondary eye will be present as descriptive summaries and listed.

For the primary and co-primary efficacy endpoints, mean change from baseline will be compared between treatment groups. The null hypothesis will be tested that there is no difference between rhNGF and vehicle in the mean overall CFB between both treatments:

$$H_0: \mu_{\text{rhNGF}} = \mu_{\text{Vehicle}}$$

$$H_1: \mu_{\text{rhNGF}} \neq \mu_{\text{Vehicle}}$$

Where μ is the mean change from baseline at considered visit within the given treatment.

This hypothesis will be tested exploratory at a 5% level of significance with an Analysis of the Covariance (ANCOVA) with treatment, respective baseline value and eye subgroup (1 vs 2 study eyes treated) in the model.

The Least-squares means estimate of the treatment effect and the treatment group difference (both with 95% confidence intervals) will be reported. P-values will be rounded to three decimal places. If a p-value is less than 0.001 it will be reported as “<0.001”. Due to the high numbers of observations, the assumption of normality is assumed.

The ANCOVA analysis will be performed for the following endpoints:

- Change from Baseline in SANDE Frequency and Severity Score at Week 8 (LOCF) for the FAS as exploratory primary efficacy analyses
- Change from Baseline in SANDE Frequency and Severity Score at Week 8 (LOCF) for the PPS as supportive to primary efficacy analyses

- Change from Baseline in SANDE Frequency and Severity Score (without imputation) at Week 8 for the FAS as supportive to primary efficacy analyses
- Change from Baseline in Corneal Staining at Week 8 (LOCF) for the FAS as exploratory to co-primary efficacy analyses
- Change from Baseline in Corneal Staining at Week 8 (LOCF) for the PPS as supportive to co-primary efficacy analyses
- Change from Baseline in Corneal Staining (without imputation) at Week 8 for the FAS as supportive to co-primary efficacy analyses

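### The main Week 8 analyses of SANDE and corneal staining use LOCF in a single-visit ANCOVA; a repeated-measures model on visits already scheduled would be a cheap improvement, valid under MAR

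*Protocol*

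**What the plan says.** Protocol 9.1.1, on SANDE: "for primary week 8 endpoint analysis, LOCF will be imputed for early end-of treatment data". Protocol 9.1.2, on corneal staining: "mean changes from baseline will be evaluated at week 8 for Co-primary endpoint analysis, LOCF will be imputed for early end-of treatment data".

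SAP 8.2 lists as the main symptom analysis "Change from Baseline in SANDE Frequency and Severity Score at Week 8 (LOCF) for the FAS as exploratory primary efficacy analyses", with a matching entry for corneal staining. The model is an "Analysis of the Covariance (ANCOVA) with treatment, respective baseline value and eye subgroup (1 vs 2 study eyes treated) in the model". It has no visit term and is fitted to Week 8 only.

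SAP 8.2 also plans the same model on observed data: "Change from Baseline in SANDE Frequency and Severity Score (without imputation) at Week 8 for the FAS as supportive to primary efficacy analyses" and "Change from Baseline in Corneal Staining (without imputation) at Week 8 for the FAS as supportive to co-primary efficacy analyses". The LOCF analyses are repeated on the per-protocol set.

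Both variables are scheduled at baseline, Week 4, Week 8 and Week 12 (Study Schedule). Under SAP 9.5.1 and 9.5.2 the Week 4 values are only summarised descriptively. They enter a model only when carried forward.

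SAP 7.2.7 carries forward the last post-baseline value, unscheduled visits included. SAP 7.1 moves a dropout's final visit to Week 4, Week 12 or Unscheduled by window (Week 4 is days 26-30) and uses unscheduled visits for imputation only. On the status of the tests, SAP 3.7 says: "These inferential procedures will be purely exploratory without adjusting for type I error rate".

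**The concern.** LOCF treats an earlier score as if it had been observed at Week 8. If patients are still improving between the visits, each dropout is recorded as less improved than he or she would have been, so the arm that loses more patients looks worse. The bias can shrink the difference, enlarge it, or create one where none exists.

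Continuing change is plausible here. The sample size text assumes improvement even on vehicle (-20 SANDE points, -2.9 NEI points), and patients enter within 6 months of surgery. Protocol 14.4.1 lists lack of efficacy and adverse events as reasons for discontinuation, so dropout may depend on outcome and differ by arm.

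The planned observed-case ANCOVA is not a full answer, because it discards the Week 4 values of the same dropouts. What is at stake is the trial's efficacy estimate and its confidence interval: neither planned analysis uses all the collected data under a missing-at-random (MAR) assumption.

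**Working it through.** **1. Planning figures (Protocol 10.2, SAP 3.6).** Two-sided 0.05, 80% power, n per equal arm = 2 x [SD x (1.960 + 0.842) / difference]^2.

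- SANDE, difference 10, SD 20: 62.8, so 63 as stated.
- Corneal NEI, difference 1.0, SD 2.2: 75.98, so 76 as stated. At 2:1 this is 114 and 57; divided by 0.95, 120 and 60.

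The plan's figures reproduce. Power at 120/60 is 0.885 for SANDE and 0.820 for NEI. The only dropout rate given is 5%, not split by arm.

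**2. LOCF shift in closed form.** Let d be the dropout in an arm and r the share of the Week 8 change already present in the carried value. Then

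LOCF arm mean = full mean x [1 - d x (1 - r)].

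The documents do not give r. I assume 0.5 to 0.7 and that every dropout carries a Week 4 value. The SANDE planning means are -30 and -20; they refer to the mean score, and I use them for either SANDE item.

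| Dropout rhNGF / vehicle | r = 0.5 | r = 0.7 |
|---|---|---|
| 5% / 5% (planned) | -29.25 + 19.50 = -9.75 | -29.55 + 19.70 = -9.85 |
| 10% / 2% (assumed) | -28.50 + 19.80 = -8.70 | -29.10 + 19.88 = -9.22 |
| 2% / 10% (assumed) | -29.70 + 19.00 = -10.70 | -29.82 + 19.40 = -10.42 |

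Against a true -10, the shift is 0.15-0.25 at the planned rate, 0.78-1.30 towards zero if rhNGF loses more patients, and 0.42-0.70 away from zero if vehicle does.

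For NEI at 5%/5% the difference is -0.975 to -0.985 instead of -1.0. At 10%/2% it is -3.705 + 2.871 = -0.834 (r = 0.5) or -3.783 + 2.883 = -0.900 (r = 0.7).

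**3. Scale.** The SE of the SANDE difference is 20 x sqrt(1/120 + 1/60) = 3.16. A shift of 0.25 is 0.08 SE. With r = 0.5 and 5%/5%, power goes from 0.885 to 0.869 for SANDE and from 0.820 to 0.800 for NEI.

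**4. No true effect (both arms -20), 10%/2%.** LOCF gives -19.0 + 19.8 = +0.8 (r = 0.5) or -19.4 + 19.88 = +0.48 (r = 0.7), against rhNGF. A shift of 0.8 is 0.25 SE and puts the nominal 0.05 error rate at about 0.057.

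**5. Comparison of methods by simulation.** 4,000 runs per scenario, 120 vs 60, SANDE SD 20, with Week 4 at 50% of the Week 8 change and a correlation of 0.6 between visits (both assumed). The repeated-measures (RM) estimate is the two-visit maximum-likelihood one. The unequal rates are assumed and well above the planned 5%.

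| Scenario (rhNGF / vehicle dropout) | LOCF | Observed cases | RM model |
|---|---|---|---|
| True -10, MAR, 20% / 10% | -7.45 (power 0.54) | -11.15 | -9.96 (power 0.85) |
| True -10, MAR, 10% / 20% | -11.14 | -8.89 | -10.09 |
| True -10, MNAR, 20% / 10% | -8.66 | not quoted | -11.36 |
| Type I error, MAR, 20% / 5% | 0.101 | 0.082 | 0.048 |
| Type I error, MNAR, 20% / 5% | 0.049 | 0.158 | 0.098 |

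At 5%/5% under MCAR or MAR, LOCF gives about -9.7 and the model about -10.0, with the same SE (3.2-3.3).

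**The case against.** - **The model is not bias-free.** It is valid under MAR. In the MNAR scenarios above it is also biased and has the higher type I error of the two. Because lack of efficacy is a listed reason for leaving, MNAR cannot be ruled out. This stands.
- **Continuing recovery is not documented.** The -30 and -20 are single assumed changes, not a trajectory. The background reports improvement after 4 weeks of rhNGF in dry eye, which fits an early plateau equally well. At r = 1 the LOCF bias is zero. This stands: the bias is conditional.
- **Not every dropout carries a Week 4 value.** The plan asks for a full Week 8 assessment at early termination, so a patient leaving on day 45 can contribute a day-45 value. For such patients r is nearer 1 and the table overstates the shift. For patients who leave before Week 4 it understates it.
- **The change is not free.** Off-window early-termination visits become Unscheduled under SAP 7.1. A model on scheduled visits alone would drop them, and would lose any full-analysis-set patient with no other post-baseline value. This stands and shapes the fix.
- **The plan already has supportive analyses and claims little.** Inference is exploratory, and observed-case and per-protocol analyses are planned. This lowers the stakes. It does not close the gap: under MAR with unequal dropout the observed-case result errs in the opposite direction to LOCF, and the plan has no MAR estimate to settle a disagreement. The per-protocol repeat keeps LOCF.

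**Conclusion.** The point holds as a modest, conditional one. LOCF in a single-visit ANCOVA is the main analysis of both endpoints, and no planned analysis uses the Week 4 and Week 8 data together. If scores still change between those visits, the difference is biased in a direction that depends on which arm loses more patients.

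At the planned 5% equal dropout the shift is 0.15-0.25 of 10 SANDE points, under a tenth of a standard error. It reaches about 0.4-1.3 points only with assumed rates of 10% and 2%. These sizes rest on r of 0.5-0.7 and on every dropout carrying a Week 4 value.

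A reader might infer more: that these patients are known to keep recovering, that a repeated-measures model removes the bias at no cost, or that the trial's conclusion is in danger. The documents support none of these. They give no trajectory, the model needs MAR and a visit-mapping rule, and at the planned dropout the effect is small in a study whose tests are labelled exploratory. The change is worth making because it is cheap, and because the direction of any LOCF bias cannot be known beforehand.

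**What to change.** - **SAP 8.2:** take the exploratory Week 8 contrast for SANDE frequency, SANDE severity and Main Eye corneal staining from a repeated-measures model on the Week 4 and Week 8 changes, with treatment, visit, treatment-by-visit, baseline, baseline-by-visit, number of study eyes and unstructured covariance. State that it assumes MAR.
- **SAP 7.1:** say how off-window early-termination and unscheduled values enter the model, so that full-analysis-set patients are not lost.
- **Sensitivity:** keep the LOCF and observed-case ANCOVAs, and add one MNAR analysis, for example a delta adjustment over a stated range.
- **SAP 7.2.7:** as LOCF stays, correct the corneal staining rule, which refers to frequency and severity (SANDE items), and state that nothing after Week 8 is carried into Week 8.
- **SAP 3.7:** list the change, since Protocol 9.1.1 and 9.1.2 name LOCF.

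Cost: SAP wording and some programming, double-programmed under SAP 5.3, settled before unmasking. No new data are needed. The downsides are a departure from the protocol's named rule and residual bias if dropout is MNAR.

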#### **9.1.2 Co-primary variable**

- Cornea vital staining with fluorescein (National Eye Institute [NEI] scales) – mean changes from baseline will be evaluated at week 8 for Co-primary endpoint analysis, LOCF will be imputed for early end-of treatment data)

#### **9.1.3 Secondary variables**

- Conjunctiva vital staining with fluorescein (National Eye Institute [NEI] scales)
- Tear Film Break-Up Time (TFBUT)
- Cochet-Bonnet corneal aesthesiometry
- Nerve count and morphology at scanning laser in vivo corneal confocal microscopy (only patients who had LASIK surgery)

Evaluations will be performed on week 4, week 8 and 4 weeks after discontinuation of treatment (week 12).

## **10 STATISTICAL METHODS**

The data documented in this study will be summarized using descriptive summary statistics, i.e. arithmetic mean, SD, CV (%), minimum, median and maximum values for quantitative variables, and frequencies for qualitative variables. In case a patient has two study eyes, its quantitative efficacy data will be regarded as within subject duplicates, allowing more precise patient values as well as the splitting of the SD into a within-subject and between-subject component.

The statistical analysis will be performed using SAS® version 9.1.3 Service Pack 4 for Windows® or higher.

A statistical analysis plan (SAP) will be issued before database lock and de-masking. Final statistical analysis on the study primary, co-primary and secondary variables will be presented in detail in the SAP.

### **10.1 Analysis Sets**

#### **10.1.1 Definitions**

A patient will be defined as screened after the signature of the informed consent, regardless of the completion of all the screening procedures.

A patient will be defined as eligible if he/she meets all the inclusion criteria and does not fulfil any of the exclusion criteria for at least one eye (defined as study eye). Otherwise he/she will be defined as a screen failure.

A patient will be defined as enrolled in the study if he/she is randomized.

- Enrolled set: all enrolled patients.
- Safety Set (SAF): all enrolled patients who receive at least one dose of the investigational medicinal product(s) at the study eye(s). This analysis set will be used for demographic, baseline and background characteristics and the safety analysis
- Full Analysis Set (FAS): all patients in the SAF, who have at least one post-baseline efficacy measurement. This analysis set will be used for the primary and co-primary efficacy analysis.
- Per Protocol set (PP): all patients in the FAS who fulfil the study protocol requirements in terms of investigational medicinal product intake and collection of primary and co-primary efficacy data and with no major deviations that may affect study results. This analysis set will be used for supportive efficacy analysis

Each patient will be coded by the CRO Biometry Unit as valid or not valid for the Enrolled Set, SAF, FAS and PP. Patients will be evaluated according to the treatment they will actually receive.

#### **10.1.2 Reasons for exclusion from the Full Analysis Set**

Reasons for the exclusion from the Full Analysis Set are the following:

- failure to take at least one dose of the IMP at any study eye
- lack of any efficacy data post enrolment
- failure to satisfy major inclusion/exclusion criteria (eligibility violations). Patients who fail to satisfy an inclusion/exclusion criterion may be excluded from the analysis without the possibility of introducing bias only under the following circumstances:
  - the inclusion/exclusion criterion was measured prior to enrolment
  - the detection of the relevant eligibility violations can be made completely objectively
  - all detected violations of the particular inclusion/exclusion criterion are excluded

### **10.1.3 Reasons for exclusion from the Per Protocol set**

Reasons for the exclusion from the Per Protocol set will be determined in the Blind Data Review Meeting and can be the following:

- lack of compliance with IMP administration (see § 10.3)
- exposure to an IMP dose different from the one assigned to the patient
- missing primary or co-primary efficacy data
- failure to satisfy any inclusion/exclusion criteria (eligibility violations)
- intake of prohibited medications

### **10.2 Sample size and power considerations**

Sample size was calculated by assuming at single eye level a mean difference from baseline mean SANDE scores of  $-30 \pm 20$  in the rhNGF groups versus  $-20 \pm 20$  in vehicle group (80% power,  $\alpha = 0.05$ ; 2-sided test), considering that the active comparator has already proven safe and effective in dry eye patients. The sample size has been calculated based on a 2:1 randomization by the following formula:

$$n_1 = (0.5) \times n \times (1 + k)$$

$$n_2 = (0.5) \times n \times (1 + (1/k))$$

with  $n_1$  = active treatment and  $n_2$  = vehicle and  $n = 63$  and  $k = n_1 / n_2 = 2/1 = 2$ . Therefore  $n_1 = 94,5$  and  $n_2 = 47,25$ . Assuming a 5% drop out rate, a total of 100 patients in the active arm and 50 in the vehicle arm are required. This calculation is based on one study eye per patient. Whereas also two study eyes per patient may occur, that will increase power to above 80%).

However, in order to provide the mean of detecting a significant difference also on a clinical sign of the effect of the rhNGF therapy (namely Co-primary Efficacy Endpoint cornea vital staining with fluorescein (National Eye Institute [NEI] scales)), sample size calculation was also performed by assuming, at single eye level, a mean difference from baseline in Cornea NEI scale scores of  $-3.9 \pm 2.2$  in the rhNGF groups versus  $-2.9 \pm 2.2$  in vehicle group (80% power,  $\alpha = 0.05$ ; 2-sided test), considering that the active comparator has already proven safe and effective in dry eye patients. The sample size has been calculated based on a 2:1 randomization by the following formula:

$$n_1 = (0.5) \times n \times (1 + k)$$

$$n_2 = (0.5) \times n \times (1 + (1/k))$$

with  $n_1$ = active treatment and  $n_2$ = vehicle and  $n= 76$  and  $k= n_1 / n_2 = 2/1=2$ . Therefore  $n_1= 114$  and  $n_2=57$ . Assuming a 5% drop out rate, a total of 120 patients in active arm and 60 in the vehicle arm are required. This calculation is based on one study eye per patient. Whereas also two study eyes per patient may occur, that will increase power to above 80%).

Considering the two calculations performed to determine the sample size, in this study will be enrolled 180 patients (120 patients enrolled in active arm and 60 in the vehicle arm) in order to detect both changes at the same time in the variables.

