No adjustment for multiplicity has been made considering that rhNGF efficacy is to be evaluated on the contemporaneous change of both variables (see ICH-E9)

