### **10.5 Analysis of ophthalmological evaluations**

All efficacy variables will be summarized for all study eye(s) together using descriptive statistics for quantitative variables, and frequencies for qualitative variables by treatment and evaluation time point. Changes from baseline (Day 0 Baseline Visit assessment) will be presented as well, if applicable.

No adjustment for multiplicity has been made considering that rhNGF efficacy is to be evaluated on the contemporaneous change of both variables (see ICH-E9).

Additional details on the analyses will be provided in the statistical analysis plan.

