3.6 Sample Size estimation

Sample size was calculated by assuming at single eye level a mean difference from baseline mean SANDE scores of -30±20 in the rhNGF groups versus -20±20 in vehicle group (80% power, alpha =0.05; 2-sided test), considering that the active comparator has already proven safe and effective in dry eye patients. The sample size has been calculated based on a 2:1 randomization by the following formula:

$$n1 = (0.5) \times n \times (1 + k)$$

$$n2 = (0.5) \times n \times (1 + (1/k))$$

with n1= active treatment and n2= vehicle and n= 63 and k= n1 /n2 = 2/1=2. Therefore n1= 94,5 and n2=47.25. Assuming a 5% drop out rate, a total of 100 patients in the active arm and 50 in the vehicle arm are required.

However, in order to provide the mean of detecting a significant difference also on a clinical sign of the effect of the rhNGF therapy (namely Co-primary Efficacy Endpoint cornea vital staining with fluorescein (National Eye Institute [NEI] scales)), sample size calculation was also performed by assuming, at single eye level, a mean difference from baseline in Cornea NEI scale scores of -3.9 ± 2.2 in the rhNGF groups versus -2.9 ± 2.2 in vehicle group (80% power, $\alpha = 0.05$; 2-sided test), considering that the active comparator has already proven safe and effective in dry eye patients. The sample size has been calculated based on a 2:1 randomization by the following formula:

$$n1 = (0.5) \times n \times (1 + k)$$

$$n2 = (0.5) \times n \times (1 + (1/k))$$

with $n1 =$ active treatment and $n2 =$ vehicle and $n = 76$ and $k = n1 / n2 = 2/1 = 2$. Therefore $n1 = 114$ and $n2 = 57$. Assuming a 5% drop out rate, a total of 120 patients in active arm and 60 in the vehicle arm are required. This calculation is based on one study eye per patient. (Whereas also two study eyes per patient may occur, that will increase power to above 80%).

Considering the two calculations performed to determine the sample size, in this study will be enrolled 180 patients (120 patients enrolled in active arm and 60 in the vehicle arm) in order to detect both changes at the same time in the variables.

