6.1 Analysis Sets

A patient will be defined as *screened* after the signature of the informed consent, regardless of the completion of all the screening procedures. A patient will be defined as screen failure, if he was screened but not enrolled in the study.

Enrolled Set:

A patient will be defined as *enrolled* in the study if he/she is randomized. This analysis set will be used for presentation of study disposition.

If not stated otherwise, analyses based on the Enrolled Set will be summarized by the treatment randomized.

Safety Set (SAF):

The Safety Set will be defined as all enrolled patients who receive at least one dose of the investigational medicinal product (IMP) at the study eye(s). *This analysis set will be used for the demographic, baseline and background characteristics and safety analysis.* All analyses based on the SAF will be summarized by the treatment received.

Full Analysis Set (FAS):

The Full Analysis Set will be defined as all patients in the SAF, who have at least one post-baseline efficacy measurement in a study eye. This analysis set will be used for the primary and co-primary efficacy analysis and all other efficacy analyses. All efficacy analyses based on the FAS will be summarized by the treatment randomized.

Per Protocol Set (PPS):

The Per Protocol Set will be defined as *all patients in the FAS who fulfill the study protocol requirements in terms of investigational medicinal product intake and collection of primary and co-primary efficacy data and with no major deviations that may affect study results.* This analysis set will be used for supportive efficacy analysis. All efficacy analysis based on the PPS will be summarized by the treatment randomized.

Each patient could either have 1 or 2 study eyes eligible for the analysis. For each patient a main (study) eye will be identified to enable a patient based presentation of analysis.

For patients with only 1 study eye (i.e. treated eye), this eye will be defined as 'Main Eye'.

For patients with 2 study eyes, the study eye with the higher corneal staining score at baseline will be considered as 'Main Eye' unless corneal staining score is not available at Week 8 Visit for this eye.

In this case, the other eye will be considered as 'Main Eye'. If both eyes are equally worse, the right eye will be the 'Main Eye'.

The eye not selected as 'Main Eye', will be called 'Secondary Eye'.

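### The claim that second study eyes raise power has no support in the SAP's tests, and the 80% power holds for each endpoint separately, not for showing SANDE and corneal staining together.

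*Protocol*

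**What the plan says.** Protocol 10.2 makes two calculations, each at 80% power and two-sided 5%. For mean SANDE it assumes changes of −30 against −20 (SD 20), giving 94.5/47.25 evaluable and 100/50 enrolled. For corneal staining it assumes −3.9 against −2.9 (SD 2.2), giving 114/57 evaluable and 120/60 enrolled. The larger number is adopted "in order to detect both changes at the same time in the variables". The synopsis and SAP 3.6 repeat this.

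Protocol 10.5 then relies on the joint aim: "No adjustment for multiplicity has been made considering that rhNGF efficacy is to be evaluated on the contemporaneous change of both variables". The synopsis says the same.

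After each calculation, protocol 10.2 and the synopsis add: "Whereas also two study eyes per patient may occur, that will increase power to above 80" per cent. In SAP 3.6 the SANDE calculation ends at "a total of 100 patients in the active arm and 50 in the vehicle arm are required", without that sentence. The staining calculation keeps it: "also two study eyes per patient may occur, that will increase power to above 80" per cent.

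The opening of protocol section 10 treats two study eyes as duplicate measurements within a patient, giving a more precise patient value. SAP 6.1 instead selects one Main Eye per patient. SAP 7.2.7, 8.2 and 9.5.2 test staining in that eye and give Secondary Eye and two-eye results descriptively.

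**The concern.** There are two separate problems in the same text.

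- **Second eyes.** A reader is told that patients with two study eyes give the trial more than 80% power. If the planned tests do not use the second eye's data, that reserve does not exist.
- **Joint aim.** The sample size is justified by detecting both effects, and the lack of a multiplicity adjustment is justified by requiring both. The power that matches this aim is the probability that both tests succeed. The documents give only the separate 80% figures and no correlation between the endpoints.

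What is at stake is a stated design property and how a mixed result is read (one endpoint positive, the other not). No estimate or safety output is affected.

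**Working it through.** **1. The plan's own figures.** Per arm at 1:1, n = 2 × (1.96 + 0.8416)² × (SD/difference)².

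- SANDE: 2 × 7.849 × (20/10)² = 62.8, so 63.
- Staining: 2 × 7.849 × (2.2/1.0)² = 75.98, so 76.
- 2:1 conversion: 0.5 × 63 × 3 = 94.5 and 0.5 × 63 × 1.5 = 47.25; 0.5 × 76 × 3 = 114 and 0.5 × 76 × 1.5 = 57.
- Dividing by 0.95 for dropout gives 100/50 and 120/60.

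All the stated sizes reproduce.

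**2. Power for each endpoint at the adopted size.** Expected z = difference / (SD × √(1/n1 + 1/n2)); power = Φ(z − 1.96). The square root is 0.1622 at 114/57 and 0.1581 at 120/60.

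| Evaluable | SANDE z | SANDE power | Staining z | Staining power |
|---|---|---|---|---|
| 114/57 | 3.082 | 0.869 | 2.802 | 0.800 |
| 120/60 | 3.162 | 0.885 | 2.875 | 0.820 |

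The noncentral t gives 0.865 and 0.796 at 114/57, so the normal approximation is adequate. Staining's 0.82 at 120/60 comes from patient numbers alone.

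**3. Power to show both, on the sizing assumptions** (unadjusted test, one mean SANDE score). This is the bivariate normal probability that both z statistics exceed 1.96. The correlation between the two changes is not documented, so a range is assumed.

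| Evaluable | Correlation 0 | 0.3 | 0.5 |
|---|---|---|---|
| 114/57 | 0.695 | 0.716 | 0.733 |
| 120/60 | 0.726 | 0.744 | 0.759 |

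Whatever the correlation, the joint figure cannot exceed the smaller separate power: 0.800 at 114/57 and 0.820 at 120/60. Protocol 2.1 remarks that symptoms after refractive surgery often do not track ocular surface signs, which points to the lower correlations.

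**4. Three tests.** SAP 7.2.7 defines two SANDE endpoints, frequency and severity, whereas the sizing used their mean. Suppose both scores and staining must all succeed, each SANDE score having a standardised effect of 0.50 (assumed). At 114/57 the power is 0.63 (correlation 0.5 between the SANDE scores, 0 with staining) to 0.71 (0.9 and 0.5).

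**5. The planned ANCOVA.** Adjusting for baseline divides the residual SD by 1/√(1 − r²), so each z becomes z/√(1 − r²), where r is the correlation between baseline and change, taken as equal for both endpoints. At 114/57, for correlation 0/0.3/0.5 between the changes:

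- r = 0.3: 0.751/0.766/0.780.
- r = 0.4: 0.794/0.806/0.817.

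The documents give no value of r.

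**6. What a second eye does under the SAP.**

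- SANDE: SAP 7.2.7 records one score per visit for both eyes together. A second eye adds nothing, and the sizing text's reference to single-eye level does not fit this endpoint.
- Staining: the ANCOVA uses one value per patient, from the Main Eye. The number of study eyes enters only as a covariate.
- Main Eye choice (SAP 6.1): with two study eyes, the eye with the higher baseline staining is chosen, "unless corneal staining score is not available at Week 8 Visit for this eye"; in that case the other eye is used. A second eye therefore affects which eye is analysed and can replace one without a week 8 value.

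**7. What the staining sentence could have meant.** If the two eyes were averaged in every patient, the SD would fall by √((1 + c)/2), where c is the between-eye correlation. At 114/57 staining power would then be 0.820 (c = 0.9) to 0.899 (c = 0.5), both assumed values. The SAP derives that average only for description, and SAP 3.7 does not list the move to a Main Eye analysis among its departures from the protocol.

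**The case against.** The strongest defence has four parts.

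- **No joint 80% is promised.** This stands. A reader might infer from the words about detecting both changes that the trial claims 80% joint power, or that the sample size is miscalculated. The documents support neither: the sizes are right and no joint figure is attached. This half is an omitted figure, not an arithmetic error.
- **The planned test is ANCOVA, so a shortfall below 80% is not established.** This also stands. With r of 0.3 to 0.4 the two-endpoint figure at 114/57 runs from 0.75 to 0.82. The 70–73% belongs to the unadjusted test used for sizing and must be labelled so.
- **Second eyes are not irrelevant.** Correct. It is tempting to say they add nothing to any planned test. SAP 6.1 rules that out: a second eye can become the Main Eye, and in the week 8 staining ANCOVA without imputation it can supply a value that would otherwise be missing. That limits data loss; it is not the increase above 80% that the text claims. The effect on power of choosing the worse eye at baseline is unknown.
- **All inference is exploratory.** SAP 3.7 says: "These inferential procedures will be purely exploratory without adjusting for type I error rate". This limits the severity. It also means the protocol's both-variables argument should not be turned into a formal success rule in SAP 8.2. The SAP sets no such rule, and it would be ambiguous with two SANDE scores. But SAP 3.6 still repeats the power claim, so exploratory status does not make the sentence true.

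**Conclusion.** The second-eye statement is unsupported as written. For SANDE it does not fit a single score per patient. For staining it fits the approach in protocol section 10 but not the Main Eye analysis that replaced it, and that replacement is not recorded. This conclusion rests on the text alone.

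The joint-power half is a disclosure point. The 80% applies to each endpoint separately. Its size depends on assumptions the documents do not supply: the correlation between the changes, whether the symptom endpoint means the mean SANDE score or both component scores, and the gain from baseline adjustment. It would be wrong to conclude that the trial needs more patients. Severity is minor.

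**What to change.** 1. Delete the second-eye power sentence for SANDE (protocol 10.2 and synopsis) and for staining (protocol 10.2, synopsis and SAP 3.6). Add to SAP 3.7 that the Main Eye analysis replaces the within-patient duplicate approach of protocol section 10.

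2. In the sample-size text of the protocol, synopsis and SAP, state that 80% power applies to each endpoint separately. Give the power to show both, with its assumptions: unadjusted test, mean SANDE score, correlation 0 to 0.5, about 70–73% at 114/57 and 73–76% at 120/60. Say whether the joint aim refers to mean SANDE or to frequency and severity separately; if all three tests must succeed, the figure is about 63–71% at 114/57 on the assumptions in step 4. Quote any ANCOVA gain only with the baseline correlation it assumes.

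The cost is a few sentences, with no added patients, data or analyses and no new success rule.
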